We propose a two-arm cluster randomized control trial evaluating the feasibility, acceptability, and preliminary impact of ANZANSI (Family economic empowerment + multiple family groups) among 100 adolescent girls and their caregivers. Specifically, this RCT aims to: 1) Refine and pilot test ANZANSI's feasibility and acceptability and its study procedures (recruitment, retention, data collection); 2) Identify barriers and facilitators to ANZANSI's implementation; 3) Estimate intervention parameters (e.g., study population variance, attrition and response rates); and 4) Examine the preliminary impact of ANZANSI (e.g. effect size) on identified outcomes for adolescent girls and their families, post-intervention initiation at 9 months (posttest) and 15 months (6 month follow-up) (see Figure 1).

Figure 1. Anzansi design

Ten schools will be randomly selected from a list of eligible schools, and randomized to one of two study arms: 1) Control arm (n=5 schools, n= 50 adolescent-caregiver dyads): 2) Treatment arm (n=5 schools, n= 50 adolescent-caregiver dyads) receiving ANZANSI (Family economic empowerment + multiple family groups) over a 9-month period. Adolescent girls in the same school will be assigned to the same study condition to avoid contamination.

We hypothesize that following the intervention, compared to the control arm, participants receiving the ANZANSI intervention (treatment arm) will have:

- improved school attendance and attitudes toward schooling;

- b.** lower mean levels of intentions to migrate; and
- c.** improved psychosocial wellbeing, social support and family functioning.

Study setting

The study will be conducted in the Northern region of Ghana, which is one of the three poorest regions in the country, with the highest incidence (81%) of multi-dimensional poverty index, highest rates (35%) of child labor, lowest rates of school attendance in the country. In the region, only 22% of the population age 15 years and older are classified as literate. Specific vulnerabilities relating to young women and girls in the region include traditional gender norms, early and forced marriages, higher rates of school dropout compared to their male counterparts, and being one of the main sending regions for unaccompanied female adolescents to major cities for work.

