Treatment arm (ANZANSI). In addition to bolstered care, participants in this arm will receive the ANZANSI intervention described earlier.

Intervention adaptation, delivery, monitoring and fidelity

Community stakeholders will be gathered and engaged in tailoring the content of the existing multiple family group manual focused on child behavioral health used in Ghana. BasicNeeds (implementation partner for the proposed study) staff already trained in this intervention delivery

used for SMART Africa will attend a refresher training before training facilitators to deliver this part of ANZANSI. Ten female facilitators will be selected from the community. Core components of the multiple family group intervention will be maintained. Intervention sessions will occur via 1-hour group meetings facilitated by two facilitators. Adapted protocols will guide the program delivery. Independent observations using rating scales will be made with a random sample of 60% of intervention sessions and used to assess the planned versus actual implementation; evaluate implementation integrity; and examine how strategies were altered to maximize effectiveness and acceptability.

Implementation Process Evaluation

Changes from the planned curriculum will be examined using process notes. Caregivers will report monthly on factors that affect their participation using an implementation checklist that assesses satisfaction and obstacles to program delivery: 1) factors interfering with adolescent girls' or family participation (e.g. insufficient time, health, stigma, competing priorities); 2) concrete obstacles (e.g. weather, transportation, sickness) and 3) site and staffing obstacles (e.g. time & space constraints). Caregivers and adolescent girls will also complete a short checklist on barriers/motivators developed for "Knowledge about the African American Research Experience" (R01MH58566; PI: [name]).

Quantitative Data Collection

Data will be collected at baseline and posttest (9 and 15 months post intervention initiation) from both adolescent girls and their caregivers (see Table 1 for measures).

Table 1. Measures

Variable	Measures
Demographics (A, C)	Demographic survey

School (A, C, S)	1) School Attitude Assessment Survey-Revised 2) School attendance reports
Work Attitudes (C)	Attitudes toward youth employment ⁵⁵
Savings (A, C, B)	1) Bank statements 2) Importance of savings 3) Confidence of savings 4) Financial literacy

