Psychosocial well-being (A)	1)Tennessee Self-Concept Scale Short Form 2)Rosenberg Self-Esteem Scale 3)Emotional Self-Efficacy Scale 4)Social Self-Efficacy Scale 5) Multidimensional Student Life Satisfaction Scale 6) Adolescent Stress Questionnaire
Family/social support (A, C)	1)Social Support Behavior Scale 2)Multidimensional Scale of Perceived Social Support
Family Relations (A, C)	1) Family Environment Scale (FES) 2) Family Assessment Measures (FAM)
Migration (A, C)	How likely they are to see themselves migrate? How like they are to send their daughters to work? Follow-up (6 months) are girls working?
Gender Attitudes (A, C)	1) Attitudes towards Women 2) Gender Norm Attitudes Scale
Future Orientation (A)	Thinking about the future
Feasibility	Recruitment rates; staff level of effort; number of screenings conducted; proportion eligible and agreed to enroll**; number of rescheduled, cancelled, missed sessions/ assessments to inform staffing needs and retention protocols for subsequent trial
Acceptability (A, C)	Client satisfaction Questionnaire (CSQ-8; to be adapted) Semi-structured interviews

A= adolescent, C= caregiver, B= bank

**Enrollment of 70% or higher will be considered feasible⁷¹

Measures that have been used in SSA are in italics

Measures that have been used in Ghana are in bold

The complete assessment battery is administered at each timepoint to inform future R01 level study, should findings warrant. The battery takes into account: 1) participant's literacy (read aloud procedures); 2) need for trust and rapport; and 3) use of local phrases/terms. Adolescents will be fluent in English, yet caregivers may be only speaking Dagbani (local language). Thus, all research assistants (RA) will be fluent in English and Dagbani, and assessments will be available in both languages (using forward/ backward translation by a certified translator). The

in-country Multiple Principal Investigator (MPI) [name] is fluent in Dagbani and will help cross-check the translated documents. The assessments will be conducted by trained RAs in a private location and take approximately 60 minutes with a 10-minute break. Content and construct validity will be conducted for measures to ensure cultural validity where necessary.

Qualitative data collection

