Upon intervention completion, randomly selected 30 dyads from the treatment arm will participate in interviews about their experiences with the ANZANSI intervention. We expect that this sample size will be sufficient in reaching theoretical saturation. Questions will be translated and back-translated by 2 team members fluent in both English and Dagbani (local language). The interviews will be conducted with caregivers and adolescent girls separately in a private place of their choosing by RAs (trained in qualitative interviewing) using pre-established semi-structured interview protocols. The interviews will focus on: 1) Experiences with the intervention and 2) Key multi-level (individual, family, contextual, and program) influences affecting program participation. Semi-structured interviews elicit richer responses⁷⁴ and will help better understand participants' processes and experiences with ANZANSI; potential processes behind key outcomes and mediating variables; and multi-level factors that may have affected their experiences. Interviews will last 1 hour and will be audio-taped. The interviews will assess intervention feasibility and acceptability, not children's psychosocial functioning. Hence, we do not expect the interviews to influence follow-up assessment.

Data analysis

Quantitative data analysis.

Feasibility. We will monitor recruitment rates and staff level of effort, number of screenings conducted, proportion eligible and agreed to enroll. Enrollment of 70% or higher will be considered feasible. We will also record number of rescheduled, cancelled and missed sessions and assessments to inform estimation of staffing needs and retention protocols for future trials.

Acceptability. We will adapt the Client Satisfaction Questionnaire (CSQ) to assess acceptability. Items include: *“How helpful was ANZANSI in addressing school dropout and intention to migrate to urban centers to work?”* and *“How likely are you to recommend ANZANSI to families whose children are at risk of migrating to urban centers to engage in child labor?”* Given the modest sample size, quantitative analyses of intervention data will be largely descriptive and concentrate on tabulating and summarizing satisfaction outcomes.

Preliminary impact. We expect that following intervention, relative to the control arm, participants in ANZANSI will have:

- a. improved school attendance and attitudes toward schooling;
- b. lower mean levels of intentions to migrate;

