- c. improved psychosocial wellbeing, social support and family functioning.

Children will be the units of analysis for the preliminary analyses. We will plot means by group over time to describe overall patterns of change. We will use linear mixed models (LMMs) to evaluate the proposed hypotheses. We will fit LMMs to ensure that all requisite information is available to perform the types of analyses typically undertaken in a formal RCT of intervention efficacy and to obtain valuable effect size information. LMMs will include random intercepts for school membership and random intercepts and slopes for subjects (three-level models).

Additional exploratory analyses will study caregivers and children jointly as the unit of analysis

via dyadic analysis methods such as actor-partner and means-and-deviation models to quantify caregiver vs. child effects and between- vs. within-dyad effects on psychological wellbeing.

Power calculations. Although the study purpose is to determine preliminary feasibility and acceptability rather than conduct formal hypothesis tests, we conducted several power analyses using NCSS PASS to supply additional information. Our power analyses assume $\alpha=.05$, power=.80, 83 participants retained at the final time point following 17% estimated attrition, and a conservative unconditional intra-class correlation coefficient (ICC) of 9.3% based on our previous SUUBI study of school going children and school attendance in Uganda. For the target enrollment proportion of 70% to assess feasibility, the width to the limit of the confidence interval is 24.4% (standardized distance: .28). For continuous standard normal variables to assess acceptability (e.g., CSQ-8), the distance from the mean to the confidence limit is .26. These distances to confidence limits are between small (.20) and medium (.50) effect sizes. For preliminary efficacy exploratory analyses with two post-baseline time points, minimum detectable standardized mean differences ranged from .56 to .69 for within-subjects correlations ranging from .20 to .80. In sum, our study is powered to detect small to medium distances to confidence limits for descriptive statistics and medium to large longitudinal analysis effects depending on the amount of within-subject correlation of responses, though, as noted previously, hypothesis testing is not the study focus.

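### The stated acceptability precision of .26 is too favourable: the CSQ-8 items rate ANZANSI, and the one arm that receives it gives about .33 to .42 at the plan's ICC, or .46 to .56 on 4 degrees of freedom

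*Combined protocol and SAP*

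**What the plan says.** Under Data analysis, Power calculations, the plan gives one precision figure for acceptability: "For continuous standard normal variables to assess acceptability (e.g., CSQ-8), the distance from the mean to the confidence limit is .26". It gives no n for that figure. The general inputs listed just before it are α = .05, "83 participants retained at the final time point following 17% estimated attrition", and an ICC of 9.3% taken from an earlier study of school attendance. The paragraph then places its confidence distances between effect sizes of .20 and .50 and repeats that description in its closing summary.

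The Acceptability paragraph gives two sample items from the adapted CSQ. One is "How helpful was ANZANSI in addressing school dropout and intention to migrate to urban centers to work"; the other asks whether the respondent would recommend ANZANSI. Table 1 lists the acceptability measures, for adolescents and caregivers, as "Client satisfaction Questionnaire (CSQ-8; to be adapted) Semi-structured interviews".

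On who receives the programme, Methods has "Treatment arm (n=5 schools, n= 50 adolescent-caregiver dyads) receiving ANZANSI" and the Study arms section says "In addition to bolstered care, participants in this arm will receive the ANZANSI intervention described earlier". Control families get usual schooling with notebooks and lunch.

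Two statements bear on who answers the CSQ. Under Quantitative Data Collection, "The complete assessment battery is administered at each timepoint", with no limit by arm. Under Qualitative data collection, the other acceptability method is confined to one arm: "randomly selected 30 dyads from the treatment arm will participate in interviews about their experiences with the ANZANSI intervention".

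**The concern.** A family that never received ANZANSI cannot meaningfully say how helpful it was, so the natural population for this summary is the treatment arm: half the dyads and half the schools. A half-width of .26 looks too small for five schools with about ten dyads each and the plan's own ICC, and it looks like a figure for the whole trial.

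In a descriptive pilot, precision is the main thing the sample size offers. Readers planning the later trial would expect a tighter satisfaction estimate than this arm can supply. The description of the distances as small to medium might also fail for acceptability.

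**Working it through.** **Inputs from the plan.** SD 1 (standard normal score); α = .05, taken as two-sided; ICC .093; 100 dyads, 50 per arm, 10 per school; 17% attrition, so 83 dyads overall, or 41.5 per arm at 8.3 per school; 5 schools per arm.

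**Formulas.** With one respondent per dyad and k dyads per school, n_eff = n / [1 + (k − 1) × ICC]. Half-width = critical value / √n_eff. The critical value is 1.96 (z), t on n_eff − 1, or t on 4 df (2.776) when five schools are treated as the independent units.

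**Reproducing .26.** An effective n of 60 reproduces all three figures printed together in the paragraph:

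- exact 95% interval at 70%: .568 to .812, width 24.4% (59 gives 24.6%, 61 gives 24.2%)
- arcsine distance from .70 to .568: .275, printed as .28
- t half-width: .258, printed as .26

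Both arms can supply that effective n: 100 / (1 + 7.3 × .093) = 59.6, which gives .254 (z) or .259 (t). This combines enrolled numbers with the retained school size, so it is a plausible origin, not a documented one. Other two-arm routes with one respondent per dyad:

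- 100 at 10 per school: 100 / 1.837 = 54.4, giving .266 (z) or .272 (t)
- 83 at 8.3 per school: 83 / 1.679 = 49.4, giving .279 (z) or .286 (t)

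**Treatment arm, one respondent per dyad.**

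| Basis | n_eff | z | t on n_eff − 1 | t on 4 df |
|---|---|---|---|---|
| 41.5 retained, 8.3 per school | 41.5 / 1.679 = 24.7 | .394 | .415 | .558 |
| 50 enrolled, 10 per school | 50 / 1.837 = 27.2 | .376 | .394 | .532 |
| 50 enrolled, 8.3 per school (mirrors the route to 59.6) | 50 / 1.679 = 29.8 | .359 | .375 | .509 |
| 50 enrolled, ICC zero | 50 | .277 | .284 | – |

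**Treatment arm, girls and caregivers pooled.** With d dyads, k per school and within-dyad correlation r, n_eff = 2d / [1 + r + (2k − 2) × ICC]. The plan gives no r, so it is varied from .093 to 1.

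| Basis | r | n_eff | z | t on n_eff − 1 | t on 4 df |
|---|---|---|---|---|---|
| d = 50, k = 10 | .093 | 36.1 | .326 | .338 | .462 |
| d = 50, k = 10 | .5 | 31.5 | .349 | .364 | .495 |
| d = 50, k = 10 | 1 | 27.2 | .376 | .394 | .532 |
| d = 41.5, k = 8.3 | .093 | 33.9 | .337 | .350 | .477 |
| d = 41.5, k = 8.3 | .3 | 31.2 | .351 | .365 | .497 |
| d = 41.5, k = 8.3 | .5 | 29.0 | .364 | .380 | .515 |
| d = 41.5, k = 8.3 | 1 | 24.7 | .394 | .415 | .558 |

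**What would rescue .26 in one arm.** With one respondent per dyad, no non-negative ICC does, since ICC zero already gives .28. With pooling, a z half-width that rounds to .26 needs an ICC of at most .044 (100 respondents, r equal to the ICC) or .018 (r = .5). With 83 respondents the limits are .033 and .001.

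**The .50 bound.** On 4 df, a half-width below .50 needs n_eff above (2.776 / .50)² = 30.8. One respondent per dyad never reaches that; pooling does so only at low to moderate r.

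**The case against.** The strongest reply is that .26 is not a slip of arithmetic. It follows from a two-arm effective n near 60, and no sentence restricts the CSQ to one arm. The battery is given at every timepoint without reference to arm, the instrument is still to be adapted, and the two items are only examples. Pooling girls and caregivers over both arms can also give .26: with 83 dyads and r = .5, 166 / (1 + .5 + 14.6 × .093) = 58.1, half-width .257 (z) or .263 (t). That the one-arm summary is inferred therefore stands. But every route to .26 at this ICC counts control families, and their answers about a programme they did not receive cannot measure its acceptability. If both arms are intended, the plan must say so and say what the controls are rating.

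Second, the plan does not commit to t on clusters minus one, and with z or t on the effective n every result stays between .20 and .50. That is correct. The 4-df figures are a small-cluster alternative, and the finding does not need them.

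Third, the ICC comes from attendance, not satisfaction, and the 17% attrition applies at the final timepoint. An earlier CSQ summary could lose fewer dyads, so .42 and .56 are upper values. Using the enrolled numbers as the favourable end covers this.

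Fourth, the consequence is small: the analysis is descriptive, with no threshold tied to .26. This limits the severity and does not make the figure right.

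**Conclusion.** The concern holds. If CSQ-8 acceptability is summarized among those who received ANZANSI, .26 is too favourable at the plan's own ICC. The attainable half-width is .33 to .42 with z or t on the effective n, about 1.25 to 1.6 times the stated value. With one respondent per dyad it is .36 to .42. On 4 df it is .51 to .56 for one respondent per dyad and .46 to .56 pooled, so the small-to-medium description then depends on the method chosen.

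This rests on three assumptions: the one-arm reading of the CSQ, the carry-over of ICC .093 to satisfaction (the plan's own choice), and, for pooling, an unknown within-dyad correlation. The exact origin of .26 is also inferred, but the conclusion does not depend on it. The figure should be corrected. No sample size, test or decision rests on it.

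**What to change.** State that CSQ-8 acceptability is summarized in the treatment arm, at which timepoint, and whether girls and caregivers are reported separately or pooled with a stated within-dyad correlation. Replace .26 with the matching half-width and print its n, ICC and degrees of freedom. For a separate summary at the final timepoint, the text could read:

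> CSQ-8 acceptability will be summarized in the treatment arm at 15 months, separately for girls and caregivers. With about 41 of each in 5 schools after 17% attrition and an ICC of .093 (effective n about 25), the half-width of the 95% interval is about .4 SD using the effective n, or about .56 SD using t on 4 degrees of freedom.

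If the 9-month posttest is chosen, recompute with the retention expected then. Keep the statement that the distances lie between .20 and .50, and the matching phrase in the closing summary, only if the chosen method supports it for acceptability.

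The cost is a few sentences and one recomputed figure. The stated precision becomes less favourable, and the small-to-medium description may be lost for this outcome. Sample size and data collection do not change.

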Handling of missing data. We will rely on direct maximum likelihood estimation (MLE) or a multiple imputation strategy to accommodate missing data, when necessary. Inclusion of cases with partial data is an important step since an intention-to-treat approach is planned to be the main analytic strategy for the primary aim focused on generating preliminary estimates of ANZANSI's efficacy. If statistical and/or clinical significance of treatment effects appear to

differ depending on the how missing data are addressed in analyses, such findings will be reported.

Qualitative data analysis. Interviews will be transcribed verbatim and translated where necessary. All transcripts will be uploaded to NVivo12 analytic software. Transcripts will be reviewed by the research team to have a broad understanding of the content and identify topics for discussion/observation. Analytic induction techniques will be used for coding. Initially, 5 randomly selected interview transcripts will be read multiple times and independently coded by the team using sensitizing concepts and identifying emergent themes (open coding). Themes will be broken down into smaller, more specific units until no further subcategory is necessary. Potential themes include barriers and facilitators at the individual- (e.g., time constraints, interest); family- (e.g., competing demands, support); program- (e.g., content relevance; interaction with other families); and contextual-levels (e.g., cultural norms). Analytic memos will be used to further develop themes/subthemes, and integrate ideas emerging from the data. Codes and the inclusion/ exclusion criteria for code assignment will be discussed as a team to finalize the codebook. Transcripts will then be coded by two investigators independently and inter-coder reliability will be established. A level of agreement between 66-97% indicates good reliability. Disagreements will be resolved through team discussions. The secondary analysis will compare themes across participants, and between caregivers and adolescent girls for similarities, differences, and relationships. Member checking, peer debriefing, and audit trail will be used for rigor.

Data Safety and Monitoring

To protect the integrity of the participants' data, the following standard procedures will be followed. First, the data collected from the study participants will be used only for the purpose

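### The printed acceptability distance (.26) and, if alpha is two-sided, the detectable differences (.56 to .69) do not follow from the stated inputs, and 24.4% is a full interval width rather than a distance to a limit

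*Combined protocol and SAP*

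**What the plan says.** All of this is in the combined protocol and SAP, mostly under Data analysis, Power calculations.

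- **Inputs.** Alpha .05 and power .80, with "83 participants retained at the final time point following 17% estimated attrition" and "a conservative unconditional intra-class correlation coefficient (ICC) of 9.3" per cent. Whether alpha is one- or two-sided is not stated. No cluster size, design effect or effective sample size is printed.
- **Design.** Methods and Participants give ten schools, five per arm, with ten girls enrolled per school.
- **Feasibility.** For a 70% enrolment proportion, "the width to the limit of the confidence interval is 24.4% (standardized distance: .28").
- **Acceptability.** For a standardized continuous score, "the distance from the mean to the confidence limit is .26".
- **Preliminary efficacy.** With two post-baseline visits, "minimum detectable standardized mean differences ranged from .56 to .69 for within-subjects correlations ranging from .20 to .80".
- **Planned model.** Under Preliminary impact, "LMMs will include random intercepts for school membership and random intercepts and slopes for subjects (three-level models").

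The paragraph describes the feasibility and acceptability figures together as distances to confidence limits lying between small (.20) and medium (.50) effects, and the efficacy figures as medium to large. It adds that hypothesis testing is not the focus of the study.

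**The concern.** A reader who puts the stated inputs into the usual design-effect calculation does not get the printed results. The printed figures agree with one another, but at an effective sample size about a fifth larger than the inputs give (60/49.4 = 1.21). The feasibility sentence also contradicts itself, because its percentage and its standardized distance cannot both describe the gap from 70% to a limit.

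These figures are the plan's only statement of how sensitive and precise the pilot is. One of the pilot's purposes is to supply effect sizes and study parameters for a larger trial, so the figures should be reproducible and should not look better than the stated inputs allow.

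**Working it through.** **Effective sample size from the stated inputs**

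- Cluster size: 83/10 = 8.3.
- Design effect: 1 + (8.3 − 1) × .093 = 1.679.
- Effective N: 83/1.679 = 49.4.

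**Which N gives the printed figures**

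For the mean of two visits with within-subject correlation r, the detectable difference is k × √[(4/N) × (1 + r)/2]. With two-sided alpha, k = 1.960 + .842 = 2.802. Solving for N:

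- .56 at r = .20: N = 2.802² × 4 × .60/.56² = 60.1.
- .69 at r = .80: N = 2.802² × 4 × .90/.69² = 59.3.

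The mean uses t/√N or z/√N, and the proportion uses the exact 95% interval.

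| Quantity | Printed | N = 60 | N = 49.4 |
|---|---|---|---|
| Detectable difference, r = .20 (two-sided z) | .56 | .560 | .617 |
| Detectable difference, r = .80 (two-sided z) | .69 | .686 | .756 |
| Distance for a mean (t) | .26 | .258 | .286 |
| Distance for a mean (z) | .26 | .253 | .279 |
| Full exact width at 70% | 24.4% | 24.36% | 26.9% |

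With t in place of z, the two-sided detectable differences at 49.4 are .63 to .77. Ignoring clustering does not explain the printed values either: N = 83 gives .48 to .58 and .22.

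The documents do not show where 60 comes from. Two routes land near it: 100/1.679 = 59.6, which puts the enrolled number over the retained-sample design effect, and 83/(1 + 4 × .093) = 83/1.372 = 60.5, which uses a cluster size of 5. Neither agrees with the stated inputs.

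**Power at the printed differences, two-sided, N = 49.4**

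- r = .20: .56/√[(4/49.4) × .60] − 1.960 = 2.542 − 1.960 = .582, power 72.0%.
- r = .80: .69/√[(4/49.4) × .90] − 1.960 = 2.557 − 1.960 = .597, power 72.5%.

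**The 24.4% figure**

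The exact 95% interval for 42/60 runs from .568 to about .812. The distances from 70% are 13.2 points below and about 11.2 above, and the full width is 24.4 points. On the arcsine scale, h = 2·arcsin√.70 − 2·arcsin√L:

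- L = .568 (the lower limit): h = .275, which is the printed .28.
- L = .700 − .244 = .456 (24.4 points taken as a distance): h = .50.

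So .28 belongs to the 13.2-point distance, and 24.4 is the full width. This part needs no assumption about sidedness or cluster size. At 49.4 the full width is about 27 points, about 14.7 below and 12.2 above 70%.

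**The case against.** **One-sided alpha.** The hypotheses are directional and sidedness is not stated. A one-sided noncentral-t calculation with 24 per arm (48 effective) gives .564 and .691, which print as .56 and .69. This stands, and it makes the finding on the detectable differences conditional on two-sided alpha. It needs the arm size rounded down: at 49.4 unrounded it gives .556 and .681. It also does not rescue the other figures. At 48 the distance for a mean is .29 (two-sided t interval) or .24 (one-sided bound), not .26, and 24.4% is not reproduced.

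**The match to 60 mixes approximations.** It uses z for the differences, t for the mean and an exact interval for the proportion. That is fair. Different software procedures could explain it, but the documents do not name them. About 60 is a back-fit, not a demonstrated input.

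**Partial cases are kept.** Handling of missing data says "Inclusion of cases with partial data is an important step". Counting 100 girls at the first follow-up and 83 at the second, the simple formula becomes k × √{4 × DE/[83 × 2/(1 + r) + 17]}. It gives .583 to .695 with DE 1.679 and .609 to .727 with DE 1 + 9 × .093 = 1.837. The gap narrows, but .56 is still not reached, and the paragraph states its own basis as 83 retained.

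**Enrolled N.** With all 100 girls and ten per school, effective N is 100/1.837 = 54.4. A Wald interval at 70% then also has a full width of 24.4%. It is still a full width, and the other figures become .59 to .72 and .27.

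**Impact.** The power work is offered as additional information in a largely descriptive pilot. That stands and limits the weight of the point.

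**Conclusion.** The point holds in this form:

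- **Acceptability distance.** It should be .28 (z) or .29 (t) on the stated inputs, not .26. This assumes a two-sided 95% interval, both arms pooled and 8.3 girls per school.
- **Detectable differences.** They should be about .62 to .76 (.63 to .77 with t) if alpha is two-sided, with about 72% power at the printed values. If alpha is one-sided, the printed range can be reproduced.
- **The 24.4% figure.** It is a mislabelled full width, whatever the other assumptions.

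The impact is minor. No decision rule or enrolment target changes, .28 to .29 still lies between .20 and .50, and the medium-to-large description survives.

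Three stronger readings are tempting, and the documents do not support them:

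- *The detectable differences must be restated as about .70 to .77.* A random school intercept implies a school effect that persists across visits. A simplified three-level formula, 2.802 × √{(4/83) × [(1 + r)/2 + 7.3 × .093]}, then gives .696 and .773. But it uses z with ten schools, omits the planned random slopes and makes no baseline adjustment. The plan does not fix those choices for its power calculation, so this is a reason to state the variance model, not a required value.
- *The acceptability figure is off by far more because only the treatment arm receives ANZANSI.* One item asks "How helpful was ANZANSI in addressing school dropout and intention to migrate to urban centers to work". For the treatment arm alone, 41.5/1.679 = 24.7 gives .39 (z) to .42 (t). The power paragraph does not say who enters the .26, so this is a question of definition, not an arithmetic error.
- *The pilot is too small.* The plan disclaims formal testing as its focus, so nothing here calls for more girls or schools.

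**What to change.** In the Power calculations paragraph:

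1. State the sidedness of alpha, the cluster size, the design effect, the effective sample size and the N at each visit.
2. Name the variance model behind the detectable differences, in particular whether the school effect is taken to persist across the two visits.
3. Rerun the figures on those inputs. On the inputs now printed, with two-sided alpha and the simple design-effect formula, they are about .62 to .76 for the detectable differences and .28 to .29 for acceptability. If a one-sided test was meant, say so and make the acceptability and feasibility figures consistent with the same effective size.
4. Relabel 24.4% as a full width and give the distance to each limit. At an effective size of 49 the full width is about 27 points, about 14.7 below and 12.2 above 70%.

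The cost is protocol wording and a rerun of the calculation. Enrolment, design and the qualitative conclusions stay as they are.

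### Open coding starts from 5 transcripts drawn without regard to informant, so in about one draw in three girls or caregivers supply at most one, although the plan compares the two groups

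*Combined protocol and SAP*

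**What the plan says.** All references are to the combined protocol and SAP.

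Qualitative data collection sets the sample: "randomly selected 30 dyads from the treatment arm will participate in interviews about their experiences with the ANZANSI intervention". It also sets the format: "The interviews will be conducted with caregivers and adolescent girls separately in a private place of their choosing". The total number of transcripts is not printed.

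Qualitative data analysis gives an ordered sequence. The team first reviews the transcripts in general terms. Open coding follows: "Initially, 5 randomly selected interview transcripts will be read multiple times and independently coded by the team". It uses sensitizing concepts and emergent themes, with candidate themes listed in advance at individual, family, program and contextual level, and memos develop the themes further. Next, "Codes and the inclusion/ exclusion criteria for code assignment will be discussed as a team to finalize the codebook". After that, "Transcripts will then be coded by two investigators independently and inter-coder reliability will be established". The last analytic step is the comparison: "The secondary analysis will compare themes across participants, and between caregivers and adolescent girls for similarities, differences, and relationships".

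No split of the five by informant type is stated. The section neither provides for nor rules out adding codes once the codebook is final.

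**The concern.** The plan names two informant groups and commits to comparing them, but the batch from which codes emerge is drawn as if all transcripts came from one population. Five is small enough that an unstratified draw will often be lopsided.

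Girls and caregivers may well describe different barriers to taking part and different experiences of the program. If open coding sees one transcript or none from a group, a theme that only that group raises may not have a code when full coding begins. An apparent similarity between the groups, or an apparent absence of a theme, could then reflect the codebook and not the interviews. What is at stake is part of Aim 2, which explores multi-level influences on participation and experience. The feasibility criterion and the mixed-model analyses do not depend on it.

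**Working it through.** The plan states no probability for this step, so there is no figure of its own to reproduce.

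**Inputs**
- Dyads interviewed: 30 (Qualitative data collection).
- Interviews per dyad: 2, because girl and caregiver are seen separately (same section).
- Implied transcripts: 30 × 2 = 60, of which 30 are from girls and 30 from caregivers. This is an inference.
- Transcripts open-coded at the start: 5, drawn at random (Qualitative data analysis). I take this as a simple random draw without replacement.

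**Formula**

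P(k girls among 5) = C(30, k) × C(30, 5 − k) / C(60, 5), with C(60, 5) = 5,461,512.

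| Girls : caregivers | Ways | Probability |
|---|---|---|
| 0 : 5 | 142,506 | 2.6% |
| 1 : 4 | 30 × 27,405 = 822,150 | 15.1% |
| 2 : 3 | 435 × 4,060 = 1,766,100 | 32.3% |
| 3 : 2 | 1,766,100 | 32.3% |
| 4 : 1 | 822,150 | 15.1% |
| 5 : 0 | 142,506 | 2.6% |

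**Results**
- At most one transcript from girls: (142,506 + 822,150) / 5,461,512 = 17.7%. By symmetry the figure for caregivers is the same.
- At most one from one of the two groups: the two events cannot occur together, so 2 × 964,656 / 5,461,512 = 35.3%.
- None from one of the two groups: 2 × 142,506 / 5,461,512 = 5.2%.
- Exactly one from one of the two groups: 35.3% − 5.2% = 30.1%.

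**Sensitivity of the 35.3% to the inferred 60**
- 25 dyads completed: 34.9%.
- 28 dyads completed: 35.2%.
- 30 girls and 25 caregivers: 36.2%.
- Binomial approximation with p = 0.5: 37.5%.

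**Effect of a change**
- Six transcripts, unstratified: 19.5%.
- Ten transcripts, unstratified: 1.2%.
- Five split 2 and 3, or six split 3 and 3: 0, by construction.

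Stratifying therefore does more than a moderate increase in the size of the batch.

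**The case against.** The strongest reply is that the five transcripts are an opening step and not the whole basis of the codebook. The general review beforehand is not limited to five. Sensitizing concepts and pre-listed themes supply codes whatever the draw. Memos carry ideas from the data forward. Member checking, peer debriefing and an audit trail are planned. Nothing forbids adding a code later. All of this stands, and it limits the conclusion.

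It does not remove the gap. The review aims at broad understanding and topics, and it is not coding. The listed themes are starting points, whereas open coding exists to find what was not foreseen. The memos are not tied to any balance between informants. The agreement range of 66-97% concerns how alike two coders apply codes and cannot show that a code is absent. The expectation of saturation is attached to the 30 dyads, not to the five transcripts.

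The threshold is also open to challenge. With five transcripts the best possible split is 3 to 2, and 30.1 of the 35.3 percentage points are 4-to-1 draws, in which the smaller group still contributes a full interview. The documents do not say that one transcript is too few. That is fair: the 35.3% measures imbalance, not the chance of a missed theme.

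Three stronger readings are tempting, and the documents do not support them:
- A reader might infer that the codebook rests on five transcripts only, so that a theme from the under-drawn group necessarily has no code. The other steps feed the codebook too, and the plan is silent on later additions, so such a theme may be missed but need not be.
- A reader might take one in three as the risk for girls in particular. For either named group it is 17.7%, about one in six.
- A reader might fault the draw for not covering every treatment school. The plan schedules no comparison of themes between schools, so that standard has no basis in it.

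**Conclusion.** The point holds as a cheap improvement of minor severity. The draw is unstratified while the planned comparison is by informant, and the two should match. One group supplies at most one of the five open-coded transcripts in 35.3% of draws and none in 5.2%.

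This rests on three assumptions: 60 transcripts, a simple random draw, and no unstated balancing by the team. The first hardly matters, since the figure stays between 34.9% and 36.2% under the shortfalls tried. If the team already intends to balance the batch or to keep the codebook open, the point reduces to writing that down.

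**What to change.** Under Qualitative data analysis, replace the simple random draw with one stratified by informant type, for example three girls and three caregivers chosen at random from six different dyads. State that new codes may be added during full coding, and that transcripts already coded will be recoded with the final codebook.

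The first change brings the chance of at most one transcript from either group to zero. The second covers themes that even a balanced batch does not show. The cost is one more transcript in the first round and possibly limited recoding. No new interviews or other data are needed.
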